4.2. Subgroups

4.2.1. Subgroups to meet primary and secondary objectives

- Compare efficacy parameters (PFS, OS) for the combined 1st line SU- 2nd line sequences according to the second line post SU :
 - SU in 1st line-Axitinib TKI in 2nd line
 - SU in 1st line- other TKI in 2nd line (sorafenib, pazopanib)
 - SU in 1st line/mTOR in 2nd line (temsirolimus, everolimus)

CCI [REDACTED]

- [REDACTED]
- [REDACTED]
- [REDACTED]
- [REDACTED]
- [REDACTED]

[figure not shown] 2);

- Incidence of other AEs (grade ≤ 2);
- Incidence of all AE per grade.
- AEs will be analyzed separately for AEs related to SU as solicited and unsolicited AE.
- **Discontinuation due to toxicity**
 - Proportion of patients who discontinued the treatment of interest, because of AEs;
 - Treatment duration until discontinuation for AEs;
- **Deaths**
 - Proportion of patients who died due to any cause, over the treatment period (including the 28 days after the treatment discontinuation) and along the study;
 - Cause of death (tumor-related, other cause).

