7. RESEARCH QUESTION AND OBJECTIVES

7.1. Objective

The primary goal of this prospective, observational Phase IV study is to provide knowledge regarding the use of SU as first line treatment as well as 2nd line SU- different sequence with respect to efficacy outcomes, adverse events and health related quality of life (QoL) in the real life setting.

Primary Objective:

To assess the impact of SU as 1st line treatment on Progression Free Survival (PFS) and on Time to Treatment Failure (TTF) for patients with adv/ mRCC.

Secondary Objective:

- To assess the Objective Response Rate (ORR) for adv/ mRCC patients receiving SU as 1st line treatment.
- To describe the usage of different doses of SU in these patients in terms of: dosing change, dosing schedules and the average dose received during the SU period treatment.

- To assess the impact of the 2nd line sequence SU- different treatment on combined PFS and TTF for patients with adv/mRCC and according to the second line post SU treatment (TK1,mTOR).
- To describe the safety of 2nd line SU-different sequence treatment and the tolerability of patients receiving it.
- To measure Quality of Life (QoL).

The study will collect data based on selection criteria for SU, including therapy management, treatment tolerance and safety among others.

Moreover, this study will collect and assess information on the sequence therapies (SU- different) used such as duration, the drivers of physician selection of particular agents as first & second lines, changes in therapy over time, dose modifications, discontinuation/interruptions of therapies, disease staging, toxicity from treatment and survival post stopping therapy.

Subsequent therapy post SU will also be documented. The following treatment outcomes will also be assessed:

- Treatment patterns (dose/duration) for SU.
- Patterns of toxicity exhibited by patients.

CCI

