5.5. Covariates

- In case of multivariate analyses, baseline characteristics will possibly be used as covariates.
- The final covariates will be selected according to the selection strategy of variables defined in the part 7.6.
- Possible, but not exclusive, baseline covariates related to SU initiation will be limited because of a retrospective part of the data collection, with:
 - Age and sex;
 - ECOG (0, 1, 2, 3, 4), Karnofsky performance status
 - MSKCC risk factors (Favorable, Intermediate, Poor)

- Medical history of hypertension (Yes, No)
- Delay from diagnosis (< 1 year from diagnosis to first metastasis detection/ \geq 1 year)
- Nephrectomy (Yes, No)
- Number of metastatic sites
- The covariates identified previously will be also explored and act as baseline for second line treatment initiation. In this case, other covariates will be:
 - The response to SU treatment in 1st line;
 - Duration of SU treatment, PFS;
 - Previous treatments for primary tumor (surgery, radiotherapy, other);
 - Additional anti-tumor treatments;

6. Handling missing values

- The majority of data will be collected with a website (except for FKSI-19 questionnaires).
- In this website, the input of certain data will be obligatory, limiting the number of missing values, particularly for endpoints.
- Regarding the descriptive analyses of each variable, it will be based on the available data (“observed-case analysis”), considering missing data as non-informative.
- The number of missing data will be documented for each analysis.
- The analysis of the primary endpoint is a survival analysis which is known to efficiently handle missing data: All patients are included in the analysis and missing data are called right-censored data.
- In case of absence of 20% data and over, for a main parameter such as ORR rate, the Hot-deck imputation method could be used. With this method, the missing value is replaced by the observed value of a patient with similar characteristics $X_1, X_2 \dots X_k$. If it does not exist such similar patient, the missing value will be amputated
- A sensitivity analysis will be conducted by the imputation of extreme values. In the one hand, analysis in the most unfavorable situation (i.e. missing data considered as failure) and in the other hand, analysis in the most favorable situation, i.e. missing data considered as success (e.g. for ORR, success is to be responder).

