7.4. Survival analysis methods

- The survival functions for PFS, TTF, TSF, and OS will be estimated with the Kaplan-Meier method. The survival function $S(t)$ is the probability that the event (treatment discontinuation, death or progression) does not occur before a specified time.
- This method will be applied to derive, survival curves, median event time and a 95% confidence interval for the median survival time (time at which half the analyzed patients have presented the event).
- Survival curves will give an idea of whether or not the groups are proportional (i.e. the survival functions are approximately parallel).
- For OS, the share of patients alive at 24 months will also be measured.
- The log-rank test of equality across strata will be used to compare survival curves for categorical variables (sub-groups of interest).
- For continuous variables, a univariate Cox proportional hazard regression will be used.
- For analyses of prognostic factors of survival time, multivariate Cox proportional hazard regressions will be performed.

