7.6. Strategy of selection of variables in multivariate models

- The strategy of selection of variables in multivariate models will be as follows:
 - Identifying baseline patient characteristics significantly associated with survival time in univariate analyses with a p-value of 0.25.
 - All these variables will be included in the model and a backward elimination will be realized (Starting with a complex model and removing terms sequentially until a final model with only explicative variables significantly associated with the survival time, adjusted each other).

8. Statistical Analysis

This chapter presents the planned statistical analyses to meet the study objectives.

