8.1. Efficacy analyses

8.1.1. Survival analyses

▪ Role:

- To meet primary and secondary objectives
- To assess the impact of SU as a first line therapy on progression free survival (PFS) and on time to treatment failure (TTF) for patients with adv/mRCC in real life setting;
- To assess the impact of the SU–other sequence on combined PFS and TTF for patients with adv/mRCC.
- To assess the Overall Survival (OS) (OS median and 24-month OS) for adv/mRCC patients receiving SU in first line followed by other sequence in 2nd line;
- To assess the time to strategy failure (TSF) for adv/mRCC patients receiving the SU–other sequence;
- To assess PFS and OS for the combined 1st line SU – 2nd line sequences according to the second line post SU (TKI, mTOR) treatment; (specific objective – “SU – TKI/mTOR” patients)

▪ Population:

- “SU – other sequence” patients
- “SU – TKI / mTOR” patients

▪ Endpoints:

- Progression Free Survival (PFS)
- Combined PFS
- Time to Treatment Failure (TTF)
- Combined TTF
- Time to Strategy Failure (TSF)

- Overall Survival (median OS and 24-month OS rate)
- **Subgroups:**
- Type of 2nd line treatment post SU: “SU – TKI / mTOR” patients (**SUT-TKI and SUT-mTOR**)
(only combined PFS and OS endpoints)
- **Statistical methods:** Survival analysis methods.
- **Method for handling missing values:** see guideline in chapter 7.

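### The second-line sequences are compared by an unadjusted log-rank test although physicians choose the drug, so differences in patient risk can be reported as differences between sequences

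*SAP*

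**What the plan says.** **The comparison.** SAP 4.2.1 sets out to "Compare efficacy parameters (PFS, OS) for the combined 1st line SU- 2nd line sequences according to the second line post SU": axitinib, other TKI (sorafenib, pazopanib) and mTOR inhibitor (temsirolimus, everolimus). SAP 8.1.1 repeats it as a subgroup of the survival analysis, "Type of 2nd line treatment post SU: “SU – TKI / mTOR” patients", for combined PFS and OS. It refers to the survival methods in general and has no covariate entry; the quality-of-life analysis in SAP 8.3 does have one.

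**The test.** SAP 7.4: "The log-rank test of equality across strata will be used to compare survival curves for categorical variables (sub-groups of interest". No risk strata are named. SAP section 4 applies a 5% threshold to all comparisons, without multiplicity adjustment.

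**How patients reach a group.** The study is non-interventional and physicians decide treatment freely (Protocol 8.1). Protocol 7.1 says the study will collect "the drivers of physician selection of particular agents as first & second lines".

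**Adjustment elsewhere in the plan.** SAP 7.4: "For analyses of prognostic factors of survival time, multivariate Cox proportional hazard regressions will be performed". SAP 5.5: "In case of multivariate analyses, baseline characteristics will possibly be used as covariates"; and, for the second line, "The covariates identified previously will be also explored and act as baseline for second line treatment initiation", adding among others response to SU and duration of SU treatment. SAP 7.6 screens variables univariately at p = 0.25, then eliminates backward, "removing terms sequentially until a final model with only explicative variables significantly associated with the survival time".

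**The concern.** A log-rank test answers whether the survival curves of the groups differ. When a physician picks the drug, the curves can differ because the patients differ, even if the drugs do not. MSKCC risk, performance status, and how well and how long the patient did on SU are all plausible reasons for choosing one class over another, and all are likely to relate to survival. The plan recognises that choice has drivers and lists suitable covariates, but does not connect them to this comparison.

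The Cox model in 7.4 does not close the gap. It is aimed at prognostic factors. The second-line group is not among the covariates visibly listed in 5.5, and nothing forces it into the model. Under 7.6 either the group or a confounder can be dropped for lack of significance, which in small groups may reflect only few events. An analyst who follows the text would report an unadjusted p-value for the sequence contrast. The direction of any bias depends on which class the higher-risk patients receive.

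**Working it through.** **Plan's own figure.** There is none for this comparison. The sample size of 140 rests on ORR precision (Protocol 8.7): 1.96 × √(0.37 × 0.63 / 140) = 0.080. That reproduces the stated ±8% but says nothing about the second-line groups. Group sizes, events and risk mixes are not given, so everything below is illustrative.

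**Step 1: hazard ratio produced by risk mix alone.** Assume no drug effect, hazards 1/2/4 for favourable/intermediate/poor risk, and non-poor patients split 50:50. Mean hazard at time zero:
- 40% poor: 0.30×1 + 0.30×2 + 0.40×4 = 2.50; 20% poor: 0.40×1 + 0.40×2 + 0.20×4 = 2.00. Ratio 1.25.
- 50% poor: 0.25×1 + 0.25×2 + 0.50×4 = 2.75; 15% poor: 0.425×1 + 0.425×2 + 0.15×4 = 1.875. Ratio 1.47.

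**Step 2: rejection rate of the planned test.** Three equal groups, one with the higher poor-risk share; exponential survival, favourable-risk median 24 months, 24 months of follow-up, no drug effect; three-group log-rank test at 5%. There were 4,000 runs per cell for the 50:50 split and 3,000 for 35:65 (favourable:intermediate among non-poor). Monte Carlo error is about ±1 to 1.5 points.

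| Per group | Split of non-poor | 40% vs 20% poor | 50% vs 15% poor | Same two settings, stratified by risk |
|---|---|---|---|---|
| 15 | 50:50 | 8% | 13% | 6–7% |
| 25 | 50:50 | 8% | 17% | 5–6% |
| 40 | 50:50 | 10% | 26% | 5–6% |
| 15 | 35:65 | 7% | 11–12% | 5–6% |
| 25 | 35:65 | 9% | 15% | 5–6% |
| 40 | 35:65 | 10% | 21% | 5% |

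With equal mixes the unadjusted test rejects in about 5–6%. Repeat runs with other baseline medians and splits stay within about one point of 8–11% and 12–26%.

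**Step 3: a second, simpler set of assumptions.** Two risk levels, poor-risk hazard ratio 2 to 3, good-risk median 20 months, censoring uniform over 12–24 months, 14 or 23 patients per group, 1,500 runs:
- Poor-risk shares 20/30/40%: 6–8%.
- 20/20/50%: 7–14%.
- 10/20/60%: 10–27%.
- Stratified by risk: 5–7% throughout.

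**Reading.** Mild imbalance in small groups adds only a few points; marked imbalance can multiply the nominal 5% several times. Adjusting for the factor that causes the imbalance removes the excess. The 40-per-group rows are an upper bound: they need 120 of the 140 patients in the three named groups, although the design also has supportive-care and other-drug pools.

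**The case against.** The strongest reply is that nobody is likely to be misled. Protocol 3.3.3 makes the results by second-line drug conditional on feasibility. Protocol 8.11 warns about causal attribution and heterogeneous patients and calls the study hypothesis-generating. Table shell 9.1 in the SAP shows MSKCC risk, histology, nephrectomy and metastatic sites by sequence, so imbalance in these will be visible. Shell 9.3 has no p-value column. SAP 5.5 lists suitable second-line covariates and describes its list as open. Parts of the SAP after 4.2.1 and 8.3 are redacted or missing, so an adjusted analysis there cannot be ruled out.

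Most of this stands, and it limits the point without removing it. A reader might infer that the plan ignores covariates altogether; 5.5 and 7.4 show that it does not. A reader might also infer that risk differences will be reported as drug differences; the documents support only that they can be, since no imbalance is known. But the SAP turns the protocol's conditional description into a comparison at a 5% threshold, and the visible sections that govern it, 7.4 and 8.1.1, contain no adjustment. Shell 9.1 displays neither ECOG nor response to or duration of SU, and displaying an imbalance does not correct the p-value.

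It is also fair to object that adjusting only for MSKCC and ECOG at first SU dose would miss what the physician knows when choosing the second drug. That objection is right, and the fix takes account of it.

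**Conclusion.** The point holds as a gap in specification. The sequence contrast is between groups formed by physician choice, the only named test for it is unadjusted, and the planned Cox model is neither aimed at it nor built to keep the group or its confounders.

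The size cannot be stated from the documents. With no drug effect, hazard ratios 1/2/4 and 15–40 patients per group, false rejection is roughly 8–11% for 40% against 20% poor risk and 12–26% for 50% against 15%, compared with about 5–6% when stratified by risk. Some assumed splits give slightly lower values, 7% and 11% at 15 per group. It would be tempting to quote the upper end as the plan's error rate; the documents do not support that, because it needs both marked imbalance and nearly all patients in the three groups. The protocol's exploratory purpose reduces the consequence, but it does not make the unadjusted p-value interpretable as a difference between sequences.

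**What to change.** In SAP 7.4 and 8.1.1, pre-specify one exploratory Cox model for the sequence contrast:

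- Force in the second-line group and a short fixed covariate set, all exempt from the selection in 7.6.
- Use MSKCC risk and ECOG, plus either duration of or response to SU, all already listed in 5.5. Limit the number of terms to what the observed events allow.
- Take covariate values at second-line start and run the clock from there. Combined PFS and OS are defined from first SU dose; keep those for the descriptive curves, because duration of SU is not known at that origin.
- Report adjusted hazard ratios with 95% confidence intervals. Label the Kaplan-Meier curves and any log-rank result descriptive.
- State that the contrast is hypothesis-generating and that residual confounding is possible.

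If events are too few for even this model, show the curves and medians with confidence intervals and no p-value.

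**Cost.** One more model on covariates the SAP already lists, and a rule for missing covariates, since Protocol 8.5 leaves fields blank when a parameter is not collected. Intervals will be wide: in a simulated four-parameter Cox model with 12 patients per group (400 runs), the 95% interval ran from the hazard ratio divided by about 2.7 to the hazard ratio multiplied by about 2.7, and type I error was about 8%. The adjusted result must therefore stay exploratory too.

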5.4. Quality of life endpoints

The analyses of the quality of life will be fulfilled based on the following endpoints, assessed every month over the SU treatment:

- **FKSI-19 score**
 - The FKSI-19 score will result of completed answers from FKSI-19 questionnaire version 4 (Functional Assessment of Cancer Therapy Kidney Symptom Index-19) presented in appendix 11.1
 - This scale assesses symptoms of importance to patients with advanced kidney cancer, with 19 items:
 - 12-item subscale about Disease Related Symptoms - Physical (DRS-P);
 - 1-item subscale about Disease Related Symptoms - Emotional (DRS-E);
 - 3-item subscale about Treatment Side Effects (TSE);
 - 3-item subscale about Function/ Well-Being (FWB).
 - This score will be assessed for each subscale and overall, as sum of item scores. Scoring guidelines are presented in appendix 11.2.
- **Change in scores from baseline**
 - This endpoint will be defined for the score mentioned above, as the difference between QoL score at baseline and at each follow up visit during SU treatment

5.5. Covariates

- In case of multivariate analyses, baseline characteristics will possibly be used as covariates.
- The final covariates will be selected according to the selection strategy of variables defined in the part 7.6.
- Possible, but not exclusive, baseline covariates related to SU initiation will be limited because of a retrospective part of the data collection, with:
 - Age and sex;
 - ECOG (0, 1, 2, 3, 4), Karnofsky performance status
 - MSKCC risk factors (Favorable, Intermediate, Poor)

- Medical history of hypertension (Yes, No)
- Delay from diagnosis (< 1 year from diagnosis to first metastasis detection/ \geq 1 year)
- Nephrectomy (Yes, No)
- Number of metastatic sites
- The covariates identified previously will be also explored and act as baseline for second line treatment initiation. In this case, other covariates will be:
 - The response to SU treatment in 1st line;
 - Duration of SU treatment, PFS;
 - Previous treatments for primary tumor (surgery, radiotherapy, other);
 - Additional anti-tumor treatments;

6. Handling missing values

- The majority of data will be collected with a website (except for FKSI-19 questionnaires).
- In this website, the input of certain data will be obligatory, limiting the number of missing values, particularly for endpoints.
- Regarding the descriptive analyses of each variable, it will be based on the available data (“observed-case analysis”), considering missing data as non-informative.
- The number of missing data will be documented for each analysis.
- The analysis of the primary endpoint is a survival analysis which is known to efficiently handle missing data: All patients are included in the analysis and missing data are called right-censored data.
- In case of absence of 20% data and over, for a main parameter such as ORR rate, the Hot-deck imputation method could be used. With this method, the missing value is replaced by the observed value of a patient with similar characteristics $X_1, X_2 \dots X_k$. If it does not exist such similar patient, the missing value will be amputated
- A sensitivity analysis will be conducted by the imputation of extreme values. In the one hand, analysis in the most unfavorable situation (i.e. missing data considered as failure) and in the other hand, analysis in the most favorable situation, i.e. missing data considered as success (e.g. for ORR, success is to be responder).
- For continuous endpoints (QoL endpoints), a mixed model for repeated measures (MMRM) will be used to analyze longitudinal data. Missing data will not be imputed. However, this analysis will be performed on all patients having a baseline value and at least one post-baseline value. The model will be valid under the assumption of data missing at random (MAR).

7. Statistical Methodology

- Statistical analysis will be performed with SPSS software (version 20 or higher).
- For descriptive and hypothesis testing purposes, the normal distribution assumption will be tested based on the overall shape of the histogram and on the result of the Shapiro-Wilk test if needed

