Appendix 3: List of covariate and outcomes in the study

Variable	Role	Operational definition
Age	Covariate	Defined as the date of birth of the participant
Gender	Covariate	Defined as the male or female sex
Ethnicity	Covariate	Defined as race of Middle Eastern, Indian, Caucasian or African descendant
ECOG	Covariate	The ECOG Scale of Performance Status describes a patient's level of functioning in terms of their ability to care for themselves, daily activity, and physical ability (walking, working, etc.)
Number of metastatic sites	Covariate	Total number of site where metastasis is detected
Nephrectomy	Covariate	Surgical removal of the kidney
MSKCC risk	Covariate	The MSKCC risk system stratifies patients with mRCC into poor-, intermediate- and favorable-risk categories based on the number of adverse clinical and laboratory parameters present
Hypertension	Covariate	Presence of high systolic blood pressure >13mmHg
Previous medical treatment	Covariate	Presence of medical treatment related to the disease prior to SU initiation
PFS	Outcome	The PFS will be defined as the time from when the patient receives the first dose of SU to the time of progression or death due to any cause, whichever occurs first
OS	Outcome	OS defined as the time from date of first SU dose to the date of death of any cause.
ORR	Outcome	The objective response rate is the percentage of patients with a complete response (CR) or a partial response (PR) according to RECIST 1.1 criteria as best response, over the SU treatment period.
TTF	Outcome	TTF is defined as the time from when the patient receives the first dose of treatment to the date of SU discontinuation
Combined PFS	Outcome	The time from when the patients receives the first dose of SU as first line, until progression or death due to any cause while on the 2nd line treatment, whichever occurs first during the 2nd line sequence treatment.
Combined TTF	Outcome	The time from when the patient receives the first dose with SU as first line, to the time of 2nd line sequence discontinuation

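### Time on sunitinib is listed as a covariate for second line although it is already contained in the sequence endpoints, and no second-line time origin or delayed entry is stated

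*SAP*

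**What the plan says.** SAP 5.5 opens conditionally: "baseline characteristics will possibly be used as covariates". It lists characteristics at SU initiation and then turns to second line: "The covariates identified previously will be also explored and act as baseline for second line treatment initiation". For that case it adds "The response to SU treatment in 1st line", "Duration of SU treatment, PFS" and "Additional anti-tumor treatments", among others. The PFS in this list is not labelled first-line, but the context implies it.

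SAP Appendix 3 defines combined TTF as "The time from when the patient receives the first dose with SU as first line, to the time of 2nd line sequence discontinuation". Combined PFS and OS in the same appendix also start at the first SU dose, and the protocol's endpoint section (3.3.3) agrees. First-line TTF runs from the first dose to SU discontinuation, which is SU duration. No endpoint with a visible definition starts at second-line initiation.

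SAP 8.1.1 analyses the combined endpoints and OS by the survival methods of section 7. SAP 7.4 includes multivariate Cox regression for prognostic factors. SAP 7.6 selects variables by "Identifying baseline patient characteristics significantly associated with survival time in univariate analyses with a p-value of 0.25", followed by backward elimination. Neither section mentions a landmark, delayed entry or a restart of the clock at second line.

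**The concern.** The covariates are fixed at the start of second line, but the outcome clock has been running since the first SU dose. A patient who spends longer on SU before second line must have a longer combined TTF, whatever second line achieves. A Cox model that includes SU duration would report this as a prognostic effect.

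What is at stake is a false message that patients with a long SU course do better on the sequence, or on second line, when the association follows from the definitions alone. The selection rule in 7.6 would not filter it out, because a built-in association passes a 0.25 screen easily.

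**Working it through.** **Plan's own figure.** The plan gives no figure on this point. Its one design calculation, 140 patients for ORR, reproduces (1.96 × √(0.37 × 0.63 / 140) = 0.080) but has no bearing here.

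**Definitions.** For a patient who starts second line:

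- Combined TTF = SU duration + any gap + time on second line. SU duration is an additive term.
- A combined PFS event occurs on second line, so combined PFS cannot be shorter than SU duration.
- Death comes after second line has started, so OS cannot be shorter than SU duration.
- First-line PFS is a lower bound in the same way when progression precedes second line.

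Example: take two patients with 5 months each on second line (assumed) and no gap. With 5.9 months on SU, combined TTF is 10.9 months; with 10.5 months on SU, it is 15.5 months. Second line did the same for both.

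**Size under no true effect.** Inputs:

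- SU duration D1: exponential, median 5.9 or 10.5 months (the community and academic figures in protocol 6.1.1).
- Second-line duration D2: exponential, independent of D1, median 3, 5 or 8 months (assumed).
- Patients drawn per run: 30, 60 or 100 (assumed), kept if second line starts before the cut-off.
- Administrative censoring: 24 to 36 months from first SU dose (September 2016 to September 2019 in the milestones, less 12 months' inclusion).
- No gap between lines; 400 runs for each of the 18 settings.

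Three Cox models were fitted with D1 per 3 months as covariate:

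1. Time D1 + D2 from the first SU dose, with no delayed entry.
2. Time D2 from second-line start.
3. Time from the first SU dose, with patients entering the risk set at D1.

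Ranges over the six combinations of medians:

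| Patients | Model 1: HR | Model 1: p<0.05 | Model 1: p<0.25 | Model 2: HR | Model 2: p<0.05 | Model 3: HR | Model 3: p<0.05 |
|---|---|---|---|---|---|---|---|
| 30 | 0.50–0.75 | 71.5–100% | 91.7–100% | 0.99–1.01 | 3.5–7.5% | 0.98–1.00 | 3.3–5.8% |
| 60 | 0.56–0.76 | 94.8–100% | 98.8–100% | 0.99–1.01 | 3.7–7.2% | 0.98–1.00 | 3.0–7.0% |
| 100 | 0.58–0.77 | 100% | 100% | 1.00–1.01 | 3.3–7.2% | 0.98–1.00 | 4.3–6.8% |

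With 400 runs, the simulation standard error of a 5% rate is √(0.05 × 0.95 / 400) = 1.1 points, so models 2 and 3 are in line with the nominal level. Both remove the artefact.

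**SU response.** Response is observed after the clock starts but is not an arithmetic part of survival time. A separate check used 60 patients and assumed that 37% respond, that responders stay on SU twice as long, and that they have no second-line advantage. It gave HR 0.66 to 0.78, with p<0.05 in 10 to 29% of runs. With the clock started at second line, the HR was 0.97 to 1.04, with p<0.05 in 4 to 6%. The effect is weaker and depends on those assumptions.

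**The case against.** The strongest reply is that no visible section commits to this model. SAP 8.1.1 has no covariate entry, whereas the quality-of-life section 8.3 does. Comparisons by second-line type are subgroup comparisons, for which 7.4 names the log-rank test. Covariate use is only possible, protocol 8.9 says Cox models may be used, and protocol 8.11 calls the study hypothesis-generating. SAP text between 4.2 and 5.4 is missing or blacked out, and time to strategy failure has no visible definition, so a second-line origin could sit in hidden text. Finally, covariates that "act as baseline for second line treatment initiation" can be read as moving the baseline to second line, which is what is wanted.

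The exploratory status stands and limits the weight of the point. The rest does not remove it. Appendix 3 is visible and fixes the origin at the first SU dose for all three defined sequence endpoints. Moving the baseline of the covariates without moving the clock is what creates the problem.

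A reader might infer more than the documents support:

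- *That all the added covariates are part of the outcome.* This is strict only for SU duration and first-line PFS. "Additional anti-tumor treatments" has no stated timing.
- *That true baseline factors are displaced, or an adjusted contrast between second-line drugs is distorted.* Neither was examined, and no adjusted drug contrast is visible in SAP section 8.
- *That significance is practically certain.* Rates above 99% in every setting appear only if censoring is ignored and the sample is generous; with censoring and 30 patients the rate falls to about 72%.

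**Conclusion.** The point holds for exploratory prognostic models of combined PFS, combined TTF and OS. It goes beyond missing detail: the listed covariates and the defined origins, used together as written, give a wrong answer for SU duration. The direction follows from the definitions. The size (HR about 0.50 to 0.77 per 3 months of SU) rests on the assumed second-line medians, patient numbers, exponential and independent durations, and censoring at 24 to 36 months. Over 90% of runs passed the 0.25 screen in every setting. The primary Kaplan-Meier estimates of first-line PFS and TTF use no covariates and are unaffected. The SAP should be changed, but this does not threaten the main result.

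**What to change.** In SAP 5.5, 7.4 and 7.6, state that:

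- Any Cox model using SU duration, first-line PFS or SU response as a covariate is fitted in patients who start second line. Time is counted either from the first second-line dose, or from the first SU dose with delayed entry at second-line start.
- Models timed from the first SU dose without delayed entry use only patient characteristics known at SU start as prognostic covariates. This rule does not remove the second-line drug grouping planned in SAP 4.2.1.
- Anti-tumor treatments given after a model's time origin are entered as time-dependent, and the timing meant in 5.5 is stated.

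The cost is SAP wording and a small amount of analysis work, using the therapy changes and discontinuation dates that the protocol already plans to record. If the clock is restarted, the time from second-line start needs a short definition; delayed entry keeps the existing endpoints. The SU-duration effect on the combined endpoints will no longer appear as an automatic finding.
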